### 7.2 Statistical Analysis

Group comparisons: Independent t-test (normal distribution) or Mann-Whitney U test (non-normal)

Correlation analysis: Pearson or Spearman correlation coefficients

Multi-omics integration: Sparse Canonical Correlation Analysis (sCCA), Principal Component Analysis (PCA)

Machine learning: Random Forest for key biomarker selection; ROC curve for diagnostic efficacy evaluation

Covariate adjustment: Age, sex, BMI, and other confounders in multivariate regression models

## 8. BIAS CONTROL AND QUALITY MANAGEMENT

### 8.1 Bias Control

Selection bias: Strict adherence to inclusion/exclusion criteria; consecutive enrollment

Measurement bias: Double-blind psychiatric evaluation; automated imaging analysis algorithms

Confounding bias: Multivariate regression adjustment for age, sex, BMI

Reporting bias: Protocol pre-registration on ClinicalTrials.gov; results reported per STROBE guidelines

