## 1. PROTOCOL SUMMARY

Title: Brain-Gut Axis Regulatory Mechanism of Anxiety and Depression in Irritable Bowel Syndrome

Study Design: Prospective, observational, case-control study

Study Duration: April 2025 – April 2026

Study Sites: Air Force Medical University, Second Affiliated Hospital (Tangdu Hospital)

Population: 100 IBS patients and 100 healthy controls (HC), aged 18–60 years

Primary Objective: To investigate the brain-gut axis regulatory mechanisms underlying anxiety and depression in IBS using 7T multimodal MRI, metagenomics, and metabolomics.

Key Assessments:

7T MRI: Structural (3D-T1WI), functional (resting-state fMRI), diffusion (DWI/DTI), and metabolic (ASL) imaging

Clinical: Rome IV criteria, symptom scores, Bristol Stool Scale

Psychological: Beck Anxiety Inventory (BAI), Beck Depression Inventory (BDI), Pittsburgh Sleep Quality Index (PSQI), cognitive assessments

Biological: Fecal metagenomic sequencing, serum and fecal metabolomics

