## 4. STUDY DESIGN AND METHODS

### 4.1 Study Design

This is a prospective, observational, case-control study conducted at Air Force Medical University, Second Affiliated Hospital.

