### 4.2 Study Population

#### Inclusion Criteria – IBS Group:

Right-handed, aged 18–60 years, education  $\geq 6$  years

Meets Rome IV diagnostic criteria for IBS:

Symptom onset  $\geq 6$  months prior to diagnosis

Recurrent abdominal pain  $\geq 3$  days/month in the last 3 months, plus  $\geq 2$  of:

- a. Improvement with defecation
- b. Onset associated with change in stool frequency
- c. Onset associated with change in stool form (appearance)

Supporting symptoms: abnormal stool frequency ( $<3$ /week or  $>3$ /day), abnormal stool form (Bristol Types 1–2 or 6–7), straining, urgency, incomplete evacuation, mucus in stool, or bloating

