#### Exclusion Criteria – IBS Group:

History of anti-anxiety/depressant medication (SSRIs/SNRIs, Chinese patent medicines, etc.)

within the past month

History of antibiotics or probiotics use within the past month

Inflammatory bowel disease (IBD), intestinal obstruction, other gastrointestinal diseases, or gastrointestinal surgery

Current or past psychiatric or neurological disorders (e.g., psychosis, brain tumors, consciousness disorders)

Severe hepatic/renal insufficiency, cardiovascular/cerebrovascular disease, or malignancy

Contraindications to 7.0T MRI:

Ferromagnetic implants (cardiac pacemaker, defibrillator, neurostimulator, aneurysm clip, cochlear implant, or any metallic foreign body)

Non-ferromagnetic implants (e.g., titanium alloy, orthopedic implants), intrauterine devices, non-removable dentures (including implants)

Metal foreign bodies in eyes or body (metal fragments, shrapnel, metal shavings), history of welding work or metallic foreign body injury

Tattoos or permanent makeup (eyebrows, lips) within the last month

Claustrophobia

Fever

Inclusion Criteria – Healthy Control (HC) Group:

Right-handed, aged 18–60 years, education  $\geq 6$  years

All physiological indices within normal range, no disease manifestations

No family history of psychiatric or neurological disorders

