#### Module 3: Psychological Evaluation

Auditory Verbal Learning Test, Color Test, Montreal Cognitive Assessment (MoCA), Memory Span Test, Beck Anxiety Inventory (BAI), Beck Depression Inventory (BDI), Pittsburgh Sleep Quality Index (PSQI)

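### Protocol Section 8.1 claims a double-blind psychiatric evaluation, which an IBS-versus-healthy-control study cannot have; at most, assessors can be masked at baseline

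*Protocol*

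**What the plan says.** Protocol Section 8.1 (Bias Control) gives one line to measurement bias: "Measurement bias: Double-blind psychiatric evaluation; automated imaging analysis algorithms". Only the first half can concern the psychological measures. The Protocol does not say who is blinded, to what, or how.

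The design is set out in Section 4.1: "This is a prospective, observational, case-control study". The Protocol Summary gives the groups as "100 IBS patients and 100 healthy controls (HC), aged 18–60 years". Under Section 4.2 a case qualifies on symptoms, starting with "Recurrent abdominal pain" and with onset at least 6 months before diagnosis. A control qualifies on "All physiological indices within normal range, no disease manifestations".

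Section 6.1, Module 3 puts two kinds of instrument together. The performance tests are "Auditory Verbal Learning Test, Color Test, Montreal Cognitive Assessment (MoCA), Memory Span Test". The mood and sleep scales are BAI, BDI and PSQI, and how they are administered is not stated. Section 6.2 repeats the anxiety and depression scales at 3 months, in the IBS group alone.

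**The concern.** In ordinary use, double-blind means that neither the participant nor the assessor knows the group. Here the group is the participant's own health status, which is the reason they were enrolled, so the participant side cannot be masked.

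This matters because anxiety and depression are the subject of the primary objective (Section 3), and BAI and BDI are the only anxiety and depression scales listed. Someone who knows they are being studied as a patient may answer such items differently from someone recruited for being healthy. A reader of Section 8.1 would believe the design guards against this. Section 8.1 also commits the study to STROBE reporting, so the claim could pass unchanged into the publication.

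**Working it through.** The claim has no figure of its own, so the check is mainly a comparison of sections.

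**1. Can the participant be masked?** No. Section 4.1 describes an observational study with no intervention or allocation to conceal. Under Section 4.2 cases are defined by long-standing symptoms of their own, and controls by being free of disease.

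**2. Can the assessor be masked?**

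| Occasion | Who is assessed | Assessor masking to group |
|---|---|---|
| Baseline | Both groups | Possible, if arranged |
| 3 months | IBS only | Not credible: anyone who knows the schedule knows the group |

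**3. What would baseline assessor masking protect?**

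| Measure | Source of the score | Protected by a masked assessor or scorer? |
|---|---|---|
| Verbal learning, Color Test, MoCA, memory span | Performance, scored by staff | Yes, on the scoring side |
| BAI, BDI, PSQI | The participant's account of their own state | No: the answers come from someone who knows their group |

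The second row does not depend on mode of administration. If an interviewer reads the items aloud, the answers still come from an unmasked participant.

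**4. Do other meanings of the phrase rescue it?** It might mean two independent masked raters, or a masked assessor plus a masked analyst. Either could be arranged at baseline, but neither is what the term normally conveys and neither changes the second row of the table.

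**5. Which analyses would a reporting shift reach?** Let M be the true mood score, X an imaging or omics measure, and b a constant added to the reported score of everyone who knows they have IBS.
- IBS-control difference in the scale: biased by b.
- Correlation within IBS: corr(X, M + b) = corr(X, M), so it is unchanged.

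**6. Illustration only.** The Protocol's single computable figure is its sample size (Section 5). With δ = 0.5, σ = 1.0, two-sided α = 0.05 and 80% power, the stated formula gives 2 × (1.960 + 0.842)² × 1.0² / 0.5² ≈ 62.8, i.e. 63. The t-test version gives 63.8, i.e. the stated 64. The blinding claim does not depend on it.

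Suppose there is no true mood difference and reporting shifts by b SD. The standard error is √(2/n), and the rejection probability is approximately 1 − Φ(1.96 − b/SE) + Φ(−1.96 − b/SE). At n = 80 and b = 0.2, SE = √(2/80) = 0.158 and b/SE = 1.265, so the probability is about 0.244.

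| n per group | b = 0.1 | b = 0.2 | b = 0.3 |
|---|---|---|---|
| 64 (stated minimum) | 8.7% | 20.5% | 39.6% |
| 80 (assumed: 100 less 20%) | 9.7% | 24.4% | 47.5% |
| 100 (stated target) | 10.9% | 29.3% | 56.4% |

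A t-test gives 9.6%, 24.2% and 47.1% at 80 per group. The values of b are assumptions with no anchor in the Protocol. The table shows only that more recruitment would not cure such a bias.

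**The case against.** The strongest reply is that one unexplained phrase is being made to carry too much. Four parts of that reply deserve an answer.

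- **The target of the phrase is inferred.** Section 8.1 speaks of a psychiatric evaluation, while Module 3 is headed as psychological. Section 4.2 also excludes psychiatric disorders, which needs some evaluation of its own. This is fair, but it does not help the plan. If the phrase refers to screening, participants still know their group, and the line then offers no safeguard for the mood scales at all.
- **A reader might infer that measurement bias is wholly uncontrolled.** The Protocol does not support that. Masked baseline scoring is possible, and automated imaging analysis is a separate measure that this point leaves untouched.
- **A reader might infer that the main result is biased, with false-positive rates such as 10%, 24% or 47%.** The Protocol does not support that either. No IBS-control contrast in BAI or BDI is named as an endpoint. The primary objective concerns mechanisms of anxiety and depression in IBS, and imaging and omics measures are not self-reports. The percentages rest on assumed shifts, and at 80 per group on an assumed sample size. They also assume no true mood difference, which is implausible when Section 2.1 says about half of IBS patients meet criteria for mood disorders. Section 5 does not tie δ = 0.5 to BAI or BDI, so setting a shift against it may compare different variables.
- **A reader might infer that mood-mechanism conclusions must be confined to within-IBS associations.** That is a debatable analysis choice that gives up the control half of the sample. It should not be mandatory.

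What remains is that the phrase is wrong as written, and nothing else in the Protocol corrects it. It is an affirmative statement in the bias-control section, not a detail left for a later document.

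**Conclusion.** The point holds as a misstated safeguard. The evaluation in Section 8.1 cannot be double-blind: participants know their group throughout, and the 3-month mood assessment covers IBS patients only. Masking of assessors or scorers is attainable at baseline, but it does not protect answers on BAI, BDI and PSQI.

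The size of any bias cannot be derived from the Protocol, and the illustrative percentages should not be used to grade the point. The practical consequence is limited to how an IBS-control difference on the three scales may be read, if one is reported. Within-IBS associations are unaffected by a shift that is constant across patients, though not by other self-report error. The conclusion rests on the ordinary meaning of double-blind and on the scale answers coming from the participant, whoever records them.

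**What to change.** In Section 8.1, replace the double-blind phrase with the masking that existing staff can deliver:

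- Verbal learning, Color Test, MoCA and memory span are scored without knowledge of group where feasible.
- Imaging and omics files are processed under coded IDs, with group withheld until quality control and feature extraction are locked.
- BAI, BDI and PSQI are stated to be unblinded, and assessors at the 3-month visit are not described as masked to group.
- Any IBS-control difference on BAI, BDI or PSQI is interpreted as open to reporting bias.

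Optionally, report within-IBS associations between the mood scales and the imaging or omics measures as a supporting analysis. This uses only the IBS half of the sample, so it complements the two-group analyses and does not replace them.

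The cost is a change of wording and minor ID-coding work. No extra participants, visits or assays are needed. The stated bias-control claim becomes weaker, but it becomes one the design can meet.

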### 8.2 Quality Management

Standard Operating Procedures (SOP): Develop SOPs for sample collection, MRI scanning, and data analysis

Training: Quarterly GCP, data management, and ethics training for research staff

Internal Audit: Semi-annual random inspection of 10% of CRFs against source data

External Oversight: Annual quality audit by third-party CRO

## 9. SAFETY MONITORING

### 9.1 Adverse Event (AE) Monitoring

Record MRI-related discomfort (e.g., claustrophobia) and biospecimen collection risks (e.g., vasovagal response)

Serious Adverse Events (SAE): Report to Ethics Committee within 24 hours; suspend study and initiate emergency protocol if necessary

### 9.2 Safety Reporting

Quarterly summary of adverse event incidence rates

Assessment of causality with study procedures

## 10. ETHICS AND REGULATORY CONSIDERATIONS

### 10.1 Ethics Review

This protocol and the informed consent form must be submitted to the Ethics Committee of the Second Affiliated Hospital of Air Force Medical University (Tangdu Hospital) for written approval before study initiation. The principal investigator must submit annual progress reports to the Ethics Committee and notify the committee in writing upon study completion or termination. Any protocol amendments require Ethics Committee approval prior to implementation, except for changes necessary to eliminate immediate hazards to subjects.

### 10.2 Informed Consent

Subjects will be invited to participate in this clinical research study, which requires collection and use of imaging data, serum, and fecal samples. Participation is voluntary. This study has been reviewed and approved by the Institutional Ethics Committee.

#### Risks and Discomforts:

This study involves ultra-high-field 7.0T MRI scanning, the most advanced submillimeter clinical MRI technology. Unlike X-ray and CT, MRI uses no ionizing radiation and can be repeated safely. No studies have demonstrated harm from MRI scanning.

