#### Compensation:

If privacy breaches or study-related injuries occur, compensation will be provided from study funds.

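### The risk text in Protocol section 10.2 gives an unqualified assurance that MRI is harmless and names no risk, at odds with the 7.0T contraindications in 4.2 and the events to be recorded under 9.1

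*Protocol*

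**What the plan says.** The Risks and Discomforts paragraph of Protocol section 10.2 has three sentences, all about MRI. The first describes the 7.0T scanner. The second is "Unlike X-ray and CT, MRI uses no ionizing radiation and can be repeated safely". The third is "No studies have demonstrated harm from MRI scanning". The opening of 10.2 describes a study "which requires collection and use of imaging data, serum, and fecal samples", so blood and stool sampling fall under the same consent.

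Three other places bear on this:

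- Section 4.2, in the IBS-group exclusions, lists contraindications to 7.0T MRI. They include "Ferromagnetic implants (cardiac pacemaker, defibrillator, neurostimulator, aneurysm clip, cochlear implant, or any metallic foreign body" and "Metal foreign bodies in eyes or body (metal fragments, shrapnel, metal shavings), history of welding work or metallic foreign body injury", as well as other implants, recent tattoos, claustrophobia and fever.
- Section 9.1 instructs staff to "Record MRI-related discomfort (e.g., claustrophobia) and biospecimen collection risks (e.g., vasovagal response" and sets out reporting of serious adverse events.
- The Compensation paragraph of 10.2 says "If privacy breaches or study-related injuries occur, compensation will be provided from study funds".

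The appendix list names an informed consent form (Appendix B) and an MRI safety screening form (Appendix C). The content of neither is shown.

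**The concern.** A paragraph headed as a statement of risks should carry at least the risks that the protocol itself recognises. This one carries none and gives a general assurance of safety instead. The assurance has no condition attached, whereas section 4.2 makes scanning conditional on a long list of exclusions.

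What is at stake is whether the consent information is accurate, and whether the protocol describes the scan in one consistent way. The safe-repeat sentence deserves particular attention because section 6.2 allows imaging to be repeated at 6 months in selected patients. Two of the contraindications in 4.2, recent tattoos and fever, are tied to the time of the scan. Being eligible at baseline therefore does not by itself settle eligibility for a later scan.

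**Working it through.** No formula applies. The protocol states no figure on this point and none has to be reproduced. The check is a comparison of texts.

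1. **Risks named in the risk paragraph.** Of its three sentences, none names a risk or discomfort of the scan, of blood drawing or of stool collection. The other parts of 10.2 that are shown (benefits, privacy, compensation, voluntary participation) do not name one either. Blood and stool testing appear there as a benefit.

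2. **Against section 9.1.** That section names two kinds of procedure risk, each with one example: MRI discomfort (claustrophobia) and sampling risk (vasovagal response). The risk text contains 0 of the 2. The two gaps differ in kind:
   - *MRI discomfort.* The risk text covers the scan, is headed as covering discomforts, and reports only safety. Section 9.1 treats discomfort from the same scan as something to record. The two passages are inconsistent.
   - *Sampling risk.* The risk text does not mention sampling. Leaving out vasovagal response is an omission and does not contradict the sentence about MRI. It counts because 10.2 itself says that serum is collected.

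3. **Against section 4.2.** A list of contraindications presupposes that the scan is unsuitable for the people on it. Such a list cannot stand beside an unconditional safety statement unless that statement is confined to people who are not on the list. The risk text has no such limit. The conflict is real, but it arises by implication: 4.2 excludes people and does not itself describe a harm.

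4. **Against the compensation paragraph.** It foresees study-related injury in general and does not mention MRI. It fits with the study carrying some risk but does not show that MRI is the source, so no weight is placed on it.

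5. **Who is affected.** Section 1 plans 100 IBS patients and 100 controls, 100 + 100 = 200, and section 6.2 puts the MRI at baseline. Patients scanned again at 6 months are among these 200 and do not add to them. Their number is not given. The contraindication list is printed under the IBS exclusions only, so step 3 applies most directly to the 100 patients, while step 2 applies to all 200.

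**The case against.** The strongest defence is that the paragraph addresses people who are being invited to take part and who would be excluded if they had a contraindication. Read that way, and coming straight after a comparison with ionizing radiation, it describes eligible participants and need not conflict with 4.2. It can also be said that recording discomfort is routine adverse-event capture, and that discomfort is not the same as demonstrated harm. Part of this stands: the conflict with 4.2 is by implication, and the most that can be said of the sentence is that it is unqualified. But the limitation to eligible people is not written down, and a paragraph on discomforts that names none is not reconciled with 9.1 by distinguishing harm from discomfort.

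A reader might infer several stronger points that the documents do not support:

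- *That scan safety rests on self-report, and that the assurance would make participants disclose less.* Items such as "history of welding work or metallic foreign body injury" are plausibly learned by asking, but no section says how contraindications are found. Appendix C is a dedicated screening form whose content is not shown, and no effect on disclosure is documented.
- *That participants consent without being told of these risks.* Appendix B is not shown, and nothing says that section 10.2 is the full wording given to participants.
- *That the no-harm sentence is false as a statement about published research.* The protocol offers no evidence either way, and the point here is internal consistency only.

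Ethics review of the consent form, required by section 10.1, is a safeguard but does not reconcile the protocol's own sections.

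**Conclusion.** The point holds within limits. The visible risk text in section 10.2 makes two unqualified safety statements and names no risk. This is inconsistent with 9.1 as regards MRI discomfort and, by implication, with the contraindications in 4.2. It also omits the sampling risk that 9.1 names.

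In size, neither of the two kinds of risk in 9.1 appears in a text that concerns all 200 planned participants and bears again on those selected for a repeat scan. No endpoint, analysis, sample size or power is affected. The matter is one of consent and safety wording, worth correcting because the correction is specific and cheap.

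The conclusion rests on the section 10.2 text as shown. If Appendix B already states these risks, the inconsistency within the protocol remains and the two texts need aligning. If Appendix B repeats the section 10.2 wording, the problem extends to the form that participants sign.

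**What to change.** - In section 10.2, delete the no-harm and safe-repeat sentences, or limit them expressly to people without the contraindications listed in section 4.2.
- State there the scan and sampling risks that section 9.1 names: MRI discomfort such as claustrophobia, and sampling risk such as vasovagal response.
- Reconcile the paragraph with 4.2 and 9.1 so that all three describe the procedures in the same way.
- Check Appendix B for the same wording and align it.
- Give any corrected text to participants already enrolled before a repeat scan. The planned start, April 2025, precedes the version date of 27 June 2025, so some may be enrolled already, although the protocol does not say so.

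The cost is one amendment to the protocol and consent text, with Ethics Committee approval before use as section 10.1 requires. A few people may decline once the risks are stated. No change to the design or analysis follows.

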#### Benefits:

Participants will receive systematic fecal and blood testing, comprehensive cognitive assessment, and ultra-high-field brain MRI. Any medical questions will be addressed with free consultation.

#### Privacy and Confidentiality:

All personal information and study data will be kept strictly confidential. Medical records will be

stored in locked cabinets accessible only to research personnel. Regulatory authorities and Ethics Committee members may review records as required by law. Published results will not disclose any individual identifying information.

